4.8 Dose Selection Analyses

The evaluation of SYNT001 based on total IgG levels and responses on the PDAI total activity score from baseline will be summarized using descriptive statistics. The number and proportion of patients that achieve the following criteria will be summarized (i) total IgG level nadir decrease by $\geq 60\%$ and $\leq 90\%$ from baseline and (ii) a PDAI total activity score of $\geq 50\%$ reduction from baseline to allow further clinical development in subject with pemphigus (vulgaris or foliaceus).

4.9 Analysis of Secondary Endpoints

4.9.1 Pharmacokinetic Analysis

PK results for SYNT001 will be summarized by cohort, visit and time point.

Descriptive statistics will be provided for the PK parameters including mean, SD, CV, median, minimum, and maximum.

For calculation of mean concentrations and generation of mean concentration-time profiles, all below the limit of quantification (BLQ) values will be set to zero except when an individual BLQ falls between 2 quantifiable values, in which case it will be omitted.

If there are values above the BLQ, but too sparse to allow full analysis, descriptive statistics will be performed on available values.

PK concentrations will be summarized descriptively at each nominal time point by cohort using n, mean, SD, percent coefficient of variation (CV%), standard error, median, minimum, maximum, geometric mean, geometric CV%.

Mean concentrations (\pm SD) of SYNT001 will be plotted on a linear and semi-logarithmic scale against nominal time points, by cohort. Individual concentration for each subject will be plotted using original scale and semi-log scale.

Study drug concentrations will be used to calculate the following PK parameters, if feasible:

Parameters	Description
C_{max}	Maximum observed plasma concentration observed directly from data
T_{max}	Time to reach maximum observed concentration directly from data
λ_z	Apparent first-order terminal elimination rate constant calculated by linear regression of the terminal linear portion of the log concentration vs. time curve
$t_{1/2}$	Terminal elimination half-life, calculated as $\ln(2)/\lambda_z$
AUC_{0-24}	AUC from time zero to 24 hours post-dose administration
$AUC_{0-\infty}$	AUC from time zero to infinity time (as $AUC_{0-t} + C_{last}/\lambda_z$, where C_{last} is the last quantifiable concentration)

Actual sampling time will be used for PK calculations. Actual sampling times that are outside the scheduled sampling times window described in [Table 4](#) will be excluded from summary statistics of PK concentrations but will still be used in the calculations of PK parameters.

The Linear Up Log Down method will be used in the computation of AUCs. The PK parameters λ_z and $t_{1/2}$ will not be presented for subjects who do not exhibit a terminal elimination phase in their concentration-time profiles.

The constant λ_z will not be assigned if one of the following happens:

1. T_{max} is or is equal to one of the 3 last data points,
2. The adjusted regression coefficient is less than 0.8,
3. The percent of $AUC_{0-\infty}$ extrapolated exceeds 20%,
4. The estimated elimination rate indicates a positive slope, or
5. The terminal elimination phase is not linear (as appears in a semi-logarithmic scale) based on visual inspection.

In cases where the constant λ_z is not assigned, the values of associated parameters (e.g., $t_{1/2}$ and $AUC_{0-\infty}$) will not be calculated.

4.9.2 Pharmacodynamic/ Disease Activity Analysis

PD samples will be collected for analyses throughout the study. Samples for each type of PD will be collected according to the schedule shown in [Table 5](#).

PD and disease activity markers will include but not limited to following information:

- Serum levels of total IgG,
- IgG subtypes (IgG1-4),
- Immunoglobulin A (IgA),
- Immunoglobulin M (IgM),
- Albumin,
- CIC
- Anti-Dsg 1 and 3 antibodies

All PD/disease activity data will be summarized by cohort and visit. Descriptive statistics of PD will include mean, SD, median, minimum, and maximum. Mean (\pm SD) of values and percentage change and absolute change from baseline will also be plotted.

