2.2 Secondary Objective and Endpoint

Secondary Objectives	Secondary Endpoints
To evaluate the efficacy of doses of SYNT001 at different dose levels and dosing regimens on pharmacodynamics (PD) biomarkers	The evaluation of PD biomarkers based on absolute serum levels and percent change from baseline of total IgG, IgG subtypes (IgG1-4), immunoglobulin A (IgA), immunoglobulin M (IgM), albumin, and CIC summarized by dose, dosing regimen and visit

Secondary Objectives	Secondary Endpoints
To determine the pharmacokinetics (PK) of SYNT001 following IV infusions at different dose levels and dosing regimen	The determination of PK parameters including half-life ($t_{1/2}$), maximum serum concentration determined directly from the concentration-time profile (C_{max}), observed time of peak serum concentration (T_{max}), area under the serum concentration-time curve from pre-dose ($time_0$) to 24 hours post-dose (AUC_{0-24}), and area under the serum concentration-time curve from pre-dose ($time_0$) to infinity ($AUC_{0-\infty}$), (Cohort 1); maximum serum concentration determined directly from the maximum serum concentration and corresponding T_{max} (Cohort 2) summarized by dose, dosing regimen, visit and time point
To assess the efficacy of doses of SYNT001 at different dose levels and dosing regimens on disease markers	
 • The assessment of pemphigus disease activity by responses on the PDAI based on absolute and percent change from baseline, summarized by dose, dosing regimen and visit. • The assessment of pemphigus disease activity by pathogenic antibody levels based on absolute and percent change from baseline of serum anti-desmoglein 1 and 3 antibody (anti-Dsg 1 and anti-Dsg 3) levels summarized by dose, dosing regimen and visit
To measure the immunogenicity of SYNT001 administered at different dose levels and dosing regimens	The immunogenicity of SYNT001 as determined by presence of anti-SYNT001 binding antibodies and neutralizing antibodies summarized by dose, dosing regimen, visit and time point

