3. STUDY OVERVIEW

3.1 Overall Study Design and Treatment Assignment

This is a multicenter, open-label safety study to determine the dose regimen of SYNT001 administered IV in subjects with pemphigus (vulgaris or foliaceus). Up to 8 subjects with a

diagnosis of pemphigus (vulgaris or foliaceus) will receive SYNT001 10 mg/kg weekly x 5 doses (Cohort 1). Up to 12 subjects with a diagnosis of pemphigus (vulgaris or foliaceus) will receive SYNT001 30 mg/kg weekly x 3 doses (Loading), followed by SYNT001 10 mg/kg every other week x 5 doses (Maintenance) (Cohort 2).

Subjects in both cohorts will complete the following periods of assessment: Screening, Treatment, and Follow-Up.

The Dose Escalation Committee (DEC) will consist of the Medical Monitor, an Independent Clinical Expert and the Sponsor Medical Lead. The DEC may request that Investigators, other experts, or members within their organization participate in the review. Additional information on the DEC’s responsibilities is provided in Protocol Section 9.5 and the DEC Charter.

An overview of the study cohorts is provided in Table 1.

Table 1. Cohort Overview

Cohort No.	No. of subjects	SYNT001 Dose	No. of Doses	Frequency of Doses
1 ^a	Up to 8	10 mg/kg	5	NA
2 ^b	Up to 12	Loading: 30 mg/kg ^c Maintenance: 10 mg/kg ^c	3 ^c 5 ^c	Weekly ^c Every other week ^{c, d}

- a. No more than 3 subjects with pemphigus foliaceus may be enrolled
- b. Two or fewer subjects with pemphigus foliaceus may be enrolled
- c. The dose, number of doses, and frequency of doses in Cohort 2 will be confirmed based on review of safety and PD evaluations, including but not limited to, dose-limiting toxicities, AEs, TEAEs, SAEs, and total IgG levels. Following Sponsor review of emerging safety, PD and efficacy data, the Loading dose may be reduced to 20 or 10 mg/kg weekly and/or the Maintenance dose may be increased to 20 or 30 mg/kg every other week and/or dose frequency may be increased to weekly.
- d. Ongoing safety and PD evaluations may result in modification of the dose and dosing regimen in Cohort 2. See Protocol APPENDIX 5 for the corresponding visit schedule.

The duration of subject participation for each cohort is as follows:

Cohort	Screening	Treatment	Follow-up	Maximum Total	
				Days	Weeks
1	≤14 days	28 days	84 days	126 days	18 weeks
2	≤14 days	84 days	56 days	154 days	22 weeks

Subjects will be enrolled at staggered intervals to facilitate adequate safety evaluation before dosing of subsequent subjects.

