4.2 Study Populations

Three sub-populations will be employed in the analysis of study data:

- The **Safety population** will consist of all subjects who received at least one dose of study drug.
- The **PD population** will consist of all subjects who received at least one dose of study drug and have post-dose PD data available.
- The **PK population** will consist of all subjects who received at least one dose of study drug and have post-dose PK data available.

Primary safety analyses will be performed on the Safety population. Demographics, subject disposition, screening, and baseline characteristics will be summarized for the Safety, PK and PD populations, where appropriate.

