4.4 Demographics and Baseline Characteristics

Demographics and baseline characteristics will be summarized descriptively by cohort and in total for the Safety population and repeated for PK and PD populations if they are different from the Safety population.

Demographic and baseline characteristics include, but are not limited to, age at informed consent, gender, race, ethnicity, body weight, body mass index (BMI), age at diagnosis of

pemphigus, pemphigus disease duration at Day 0, type of pemphigus, type of tissue-based test positive for pemphigus, tissue-based test positive for pemphigus duration at Day 0, current exacerbation duration at Day 0.

Continuous variables (e.g., age, weight, and BMI) will be summarized by descriptive statistics. Categorical variables (e.g., gender, race, and ethnicity) will be summarized by the number and percentage of patients in corresponding categories.

Baseline is defined as the Day 0 (pre-dose) measurement. If missing, the last measurement prior to the first study drug administration will be used as the baseline value.

Medical/surgical history will be coded using the Medical Dictionary for Regulatory Activities (MedDRA 19.1) and summarized for the number and percentage for each System Organ Class (SOC) and preferred term by cohort and in total for the Safety population.

A summary table for categories of protocol deviations will be produced for major protocol deviations. Protocol deviations will also be listed for the Safety population.

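### Percent change in anti-Dsg 1 and anti-Dsg 3 is averaged over all subjects with PD data, with no baseline-positivity restriction or low-baseline rule, so subjects lacking an antibody would dilute the mean and inflate its SD

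*SAP*

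**What the plan says.** SAP Section 2.2 defines the pathogenic-antibody secondary endpoint as disease activity "based on absolute and percent change from baseline of serum anti-desmoglein 1 and 3 antibody" levels, by dose, regimen and visit. Section 4.9.2 lists anti-Dsg 1 and 3 among the PD and disease activity markers and gives one rule for all of them: "All PD/disease activity data will be summarized by cohort and visit". On statistics it says "Descriptive statistics of PD will include mean, SD, median, minimum, and maximum". On figures, the mean (±SD) of "values and percentage change and absolute change from baseline will also be plotted".

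The PD population in Section 4.2 "will consist of all subjects who received at least one dose of study drug and have post-dose PD data available". Baseline antibody status plays no part in it. Section 3.1 pools pemphigus vulgaris and foliaceus within each cohort: up to 8 subjects in Cohort 1 (at most 3 foliaceus) and up to 12 in Cohort 2 (at most 2 foliaceus). Among the baseline characteristics, Section 4.4 lists "type of tissue-based test positive for pemphigus". The SAP states no anti-Dsg level for entry.

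The only rule for values below quantification is in Section 4.9.1 and covers drug concentrations. Table 2, footnote g, has a provision for tetanus and VZV titres below detection at baseline. Anti-Dsg has no counterpart to either.

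**The concern.** Percent change is informative only when there is something at baseline to fall. Two antibodies are analysed separately, so a subject who lacks just one of them still enters that antibody's summary.

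- If the baseline is exactly zero, percent change is undefined, and the SAP does not say whether the subject is dropped or given a value.
- If the baseline is small but positive, percent change is a ratio of two values near the assay's lower end. It cannot go below -100% but has no upper bound, so noise pushes the mean upwards, which is the direction that hides a fall.
- If such a subject simply does not change, the contribution is 0% and the mean is diluted.

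At stake is how clearly the study shows an effect on the pathogenic antibodies. With at most 8 and 12 subjects per cohort, two or three uninformative values matter. A low-baseline rule chosen after the data are seen would also be open to question.

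**Working it through.** The SAP gives no anti-Dsg figure to reproduce: no expected fall, assay scale, cut-off or frequency of antibody-negative subjects, and Section 5 reports no formal sample size calculation. The check therefore uses cohort sizes from the SAP and assumptions for the rest.

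**Inputs**
- N = 8 and N = 12 (SAP Section 3.1 and Table 1).
- Number negative for a given antibody, k: assumed, from 1 up to 3 of 8 and 2 of 12. The upper values borrow the foliaceus caps as illustrative counts only. The SAP does not say that foliaceus subjects lack either antibody, and the caps do not limit negativity among vulgaris subjects.
- True fall in positive subjects: 50%, assumed.

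**Dilution.** If negatives do not change, mean = (N − k) × (−50) / N. With every positive at −50% and every negative at 0%, the SD is zero without negatives and, with them, 50 × √[k(N − k) / (N(N − 1))].

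| N | k | Mean % change | SD due to mixing alone |
|---|---|---|---|
| 12 | 1 | 11 × (−50)/12 = −45.8 | 14.4 |
| 12 | 2 | 10 × (−50)/12 = −41.7 | 50 × √(20/132) = 19.5 |
| 8 | 1 | 7 × (−50)/8 = −43.8 | 17.7 |
| 8 | 2 | 6 × (−50)/8 = −37.5 | 23.1 |
| 8 | 3 | 5 × (−50)/8 = −31.3 | 50 × √(15/56) = 25.9 |

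If the positives also vary with an assumed SD of 20 points, the overall SD becomes 26.6 (2 of 12) and 30.0 (3 of 8).

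**What a change of sign needs.** The average rise in negatives that brings the mean to zero is (N − k) × 50 / k: 10 × 50/2 = 250% for 2 of 12, 5 × 50/3 = 83% for 3 of 8, and 550% and 350% for a single negative in 12 and in 8.

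**Can noise produce that?** Simulated with negatives at 3 ± 2 units, a floor of 0.5 units and positives at −50% with SD 20 points (all assumed), varying the correlation between a subject's baseline and follow-up values:

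| Correlation | Expected mean, 2 of 12 | 3 of 8 | 5 of 12 |
|---|---|---|---|
| 0 | −28% | −1% | +4% |
| 0.5 | −35% | −17% | −13% |
| 0.8 | −39% | −25% | −23% |

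The expected mean turns positive only with independent near-zero draws and about 40% of subjects negative. A second set of assumptions (true fall about 58%, independent draws, SD 1 unit, floor 0.1) gives a cohort mean at or above zero in about 22% (3 of 8) and 9% (2 of 12) of simulated cohorts when negatives average 2 units, but in 0.1% or fewer when they average 5 units. Even then the typical mean is about −35% and −48%.

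**Median.** With a uniform fall the median stays at the true value in every row of the first table. With spread among positives it moves somewhat: in the second set of simulations it averages about −48% to −52% for 3 of 8 and about −57% for 2 of 12.

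**After restriction.** Limited to baseline-positive subjects, the mean is −50% whatever the negative subjects' values do.

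**The case against.** The strongest objection is that the premise lies outside the SAP. Entry criteria belong to the protocol, and Tables 2 and 3 draw anti-Dsg at screening, so an antibody entry criterion cannot be excluded. The tissue-based test in Section 4.4 is a baseline descriptor and says nothing about serum status. This stands: the number of negatives is an assumption. If every subject were positive for both antibodies, the problem would not arise.

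Second, a reader might infer that the planned mean would hide the fall altogether or show a rise. The documents do not support that. They give no assay scale or noise level, and the calculations produce a change of sign only when negative subjects have very low, noisy baselines or are numerous. Dilution and a wider SD are what hold across the assumptions tried.

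Third, protection already exists. Section 4.9.2 tabulates median, minimum and maximum, absolute change is reported, and Section 4 lists all clinical data. This stands for the tables. It does not reach the percent-change figure, which is specified as mean ±SD, and absolute change does not repair a percent-change endpoint.

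Fourth, the endpoint is descriptive, dose selection (Section 4.8) rests on total IgG and PDAI, and the programming specifications (Section 6) are finalised before database lock. All true, and this limits the consequence. But who enters a secondary-endpoint summary is an analysis rule and belongs in the SAP.

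**Conclusion.** The point holds in a limited form. As written, the SAP averages and plots percent change in each anti-Dsg antibody over everyone with PD data, without a baseline-positivity restriction or a rule for zero or near-zero baselines. If some subjects lack an antibody, the mean understates the fall among those who have it. For an assumed 50% fall and unchanged negatives it is about −42% (2 of 12 negative) or −31% (3 of 8), with a between-subject SD of 19 to 26 points created by the mixture alone. These sizes rest on assumed counts of negatives and an assumed fall, and the SAP supplies neither. The effect is confined to a descriptive secondary endpoint and mainly to its mean-based displays; the dose-selection criteria are untouched.

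**What to change.** In SAP Section 4.9.2, before database lock:

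- For each antibody separately, tabulate and plot percent change only in subjects positive at baseline by the central laboratory's cut-off, and show that n at each visit.
- In the percent-change figure, plot the median, which is already tabulated, beside the mean ±SD.
- For subjects negative at baseline, report absolute values and any conversion to positive.
- State how anti-Dsg values below the assay limit are handled.

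The cost is SAP wording and a filter on data already planned, since anti-Dsg is measured at screening and Day 0 in both cohorts (Table 5). The downside is a smaller n for each antibody. If all subjects prove positive for both, the restriction changes nothing.

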4.9.3 Immunogenicity Analysis

Immunogenicity results including anti-SYNT001 antibody, anti-SYNT001 neutralizing antibodies and anti-SYNT001 antibodies titer available at the time of the database lock will be summarized by cohort, visit and time point. Descriptive statistics will include mean, SD, CV, median, minimum, and maximum.

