3.1.11 Immunogenicity Testing

SYNT001 is being developed for the acute and chronic therapy of autoimmune disorders. Although SYNT001 is a humanized IgG4 mAb, exposure to SYNT001 in clinical trials could result in the development of ADAs, with potential consequences ranging from neutralization with possible lessening of drug efficacy to safety consequences such as allergic reactions.

Testing will first detect binding ADAs. Then, for all confirmed positive samples, an ADA titer will be determined and there will be testing for neutralizing antibodies using a validated cell-based assay.

3.1.12 12-Lead Electrocardiogram (ECG)

On dose administration days, digital 12-lead ECG measurements will be obtained at 5 minutes after the completion of the infusion. When ECGs are to be collected at the same time point as a blood collection, ECGs should be collected first. All ECGs are to be performed with the subject in a supine position having rested in this position for at least 5 minutes before each reading. ECGs are to be performed in triplicate, each at an interval of 1 to 2 minutes apart (Cohort 1) or approximately 1 minute apart (Cohort 2). See [Table 4](#) for timing window allowances with respect to performing ECG.

The following ECG parameters will be collected: PR interval, RR interval, QRS interval, and QT interval. The ECG findings will be evaluated by a qualified physician for the presence of abnormalities (qualitative assessment). The physician will assess each ECG as normal, abnormal/not clinically significant, or abnormal/clinically significant.

Normal corrected QT interval using Fridericia's formula (QTcF) is ≤ 450 msec.

Abnormalities in the ECG that appear following therapy or that result in clinical signs and symptoms are considered clinically significant for the purposes of this study and will be recorded on the AE eCRF.

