4.1 General Design

All clinical data captured will be provided in data listings. Subject disposition, demographic information, and baseline characteristics will be presented. Baseline will be defined as the last value obtained prior to the first dose of study drug. Results will be summarized by dose and dosing regimen (cohort), and in total. Any discrepancy between treatment to be given and treatment received will be accounted for in these displays.

Continuous data will be summarized using descriptive statistics: number of subjects (N), number of observations (n), mean, median, standard deviation (SD), minimum, and maximum.

Categorical data will be summarized using frequencies and percentages. When categorical data will be presented, the percent will be suppressed when the count is zero to draw attention to the non-zero counts. The denominator for all percentages, unless otherwise specified, will be the number of subjects in the specified analysis population.

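### Section 4.9.3 names only continuous statistics for antibody results, plans no per-subject rate of new positives, and has no rule for results outstanding at database lock

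*SAP*

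**What the plan says.** SAP section 2.2 sets the endpoint: "The immunogenicity of SYNT001 as determined by presence of anti-SYNT001 binding antibodies and neutralizing antibodies summarized by dose, dosing regimen, visit and time point". Section 3.1.11 describes a sequence: binding antibodies are tested first, and then "for all confirmed positive samples, an ADA titer will be determined and there will be testing for neutralizing antibodies".

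Section 4.9.3 takes binding antibody, neutralizing antibody and titre together and limits them to what exists at lock: "anti-SYNT001 antibodies titer available at the time of the database lock will be summarized by cohort, visit and time point". Its only statement about statistics is "Descriptive statistics will include mean, SD, CV, median, minimum, and maximum". It names no analysis population, no subject-level count across visits, no rule on baseline status and no rule for pending results.

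The general rules that bear on it are:
- Section 4.1: "Categorical data will be summarized using frequencies and percentages". By default, percentages are taken over all subjects in the analysis population in use.
- Section 4: missing data are not imputed unless stated, and all captured clinical data are listed.
- Section 4.2: the populations are Safety, PD and PK only.

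**The concern.** Two of the three results are positive or negative, and the listed statistics do not describe such data. The same list stands in section 4.9.1 for PK parameters, where it fits. Elsewhere the SAP says plainly when it wants counts (sections 4.8, 4.9.4 and 4.10.2).

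Three things are at stake in a trial with at most 8 and 12 subjects per cohort:
- A reader of the report will want to know how many subjects developed antibodies after dosing. By-visit rows do not answer that.
- An arithmetic mean and CV of titres can be set by one subject.
- The lock clause, which no other analysis section of the SAP contains, can drop results selectively, because the later assays are run only on positives.

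**Working it through.** The SAP states no antibody rate and no sample-size calculation, so there is no figure of its own to reproduce. All counts and titres below are assumed for illustration. The cohort sizes (up to 8 and up to 12) are from section 3.1 and the sampling days from Tables 2 and 3.

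**1. Do the named statistics describe presence?** Code positive as 1 and negative as 0, a coding the SAP does not state. With 3 positives of 12:
- mean = 3/12 = 0.25
- SD = √[12 × 0.25 × 0.75 / 11] = 0.452
- CV = 0.452/0.25 = 180.9%
- median = 0

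Only the mean carries information, and it is simply the proportion. With no positives the CV is undefined. The section 4.1 default, n (%), is the form that works.

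**2. Does n (%) by visit give the share who become positive?** Post-baseline samples fall on 5 days in Cohort 1 (Days 14, 28, 56, 84, 112) and 10 in Cohort 2 (Days 7, 14, 28, 42, 56, 70, 84, 91, 112, 140). Suppose three of 12 Cohort 2 subjects are negative on Day 0 and each positive once, at different visits:
- highest by-visit figure: 1/12 = 8.3%
- subjects ever positive after dosing: 3/12 = 25.0% (exact 95% interval 5.5% to 57.2%)

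A subject already positive on Day 0 who stays positive adds one to every later row and cannot be told apart there from a new positive.

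**3. Titres.** Take three positives with titres 20, 40 and 5120:
- arithmetic mean = 5180/3 = 1727, with CV 170%
- geometric mean = (20 × 40 × 5120)^(1/3) = 4,096,000^(1/3) = 160
- median = 40

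Section 4.9.1 already plans geometric mean and geometric CV for PK concentrations, so the method is not foreign to this SAP.

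**4. Results pending at lock.** Suppose 4 of 12 subjects are confirmed binding-positive, two have a positive neutralizing result and two are pending. With no imputation and all 12 in the denominator:
- reported: 2/12 = 16.7%
- possible truth: from 2/12 = 16.7% (neither pending result positive) to 4/12 = 33.3% (both positive)

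The error can go only downward, because a pending result is counted as not positive. Each pending result that would have been positive moves the rate by 1/12 = 8.3 points in Cohort 2 and 1/8 = 12.5 points in Cohort 1.

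Removing the two pending subjects from the denominator gives 2/10 = 20.0%. That stops counting them as negative. It does not settle the rate, because the subjects removed are all confirmed positives; the range 16.7% to 33.3% should stand beside it.

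**The case against.** The strongest reply is that the plan does deliver its endpoint. Section 2.2 itself asks for a summary by visit and time point. Section 4.1 sends positive/negative results to frequencies and percentages. The list in 4.9.3 says what the statistics include, not that they are limited to these, and can be read as meant for the titre. This stands. A reader might infer that 4.9.3 fails to give the stated endpoint, and the documents do not support that. By-visit display is what the endpoint requests; the fault is that nothing else is planned.

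A reader might also infer that the trial cannot state a treatment-emergent rate. That goes too far as well. Both cohorts have a Day 0 sample and repeated later ones, captured data are listed, and section 1 allows supplementary analyses. The rate could be derived afterwards. It would then be an unplanned count, with its definition chosen once the data are known.

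On the lock clause, nothing says that lock will come before the assays are finished, and no turnaround times are given, so the clause may exclude nothing. Late samples awaiting the first binding test would be pending whatever their status. Binding positives already reported stay in. This is all fair, and the bias is conditional.

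On titres, median, minimum and maximum are already listed, so a reader would see the skew. Only the geometric mean would be new.

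Finally, Protocol Section 7.5.6 and the separate programming specifications may hold definitions. They are not shown. But section 1 says the SAP supersedes the protocol's statistical considerations, and 4.9.3 is where the statistics and the lock rule are fixed.

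**Conclusion.** The point holds in limited form. Section 4.9.3 names statistics that do not suit two of its three results and leaves the presence analysis to a general rule. That rule meets the endpoint wording visit by visit, but no planned table shows how many subjects become positive after dosing, or separates them from Day 0 positives. In the illustration the highest by-visit figure is 8.3% where the per-subject figure is 25.0%.

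The lock clause, together with a denominator of all subjects, can understate the neutralizing rate, by 8.3 or 12.5 points for each missed positive. This assumes that results are outstanding at lock and that the section 4.1 denominator applies, since 4.9.3 sets no other. It would be wrong to say that the rate is biased as planned; the text allows the bias but does not bring it about.

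The endpoint is secondary and descriptive, and neither the safety nor the dose-selection conclusion depends on it. The wording is still worth changing, because the repair is small and the samples are already scheduled.

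**What to change.** Rewrite section 4.9.3 as follows:
- **Presence:** n/N (%) of subjects binding-positive and neutralizing-positive, by cohort and visit.
- **Treatment-emergent:** n/N (%) of subjects negative on Day 0 and positive later, or with a rise from a positive baseline that is set in advance. The denominator is subjects with a Day 0 result and at least one post-dose result. Show Day 0 positives separately.
- **Titre:** in positives only, median, range and geometric mean in place of arithmetic mean and CV.
- **Lock:** lock after all binding, titre and neutralizing results are received. Failing that, report the number outstanding by assay, exclude those subjects from the denominator, and give the lowest and highest rate that the pending results allow.

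The cost is SAP wording, one extra table and possibly a short delay to lock while the last assays are completed. No new samples are needed.
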